**INSTRUCTIONS:**

- *Use this template to prepare your IRB Protocol.*
- *Depending on the nature of what you are doing, some sections may not be applicable to your research. If so, please mark as N/A.*
- *When you write a protocol, keep an electronic copy. You will need to modify this copy when making changes.*
- *Consider using a different color font for your answers.*

**PROTOCOL TITLE:**

*Include the full protocol title.*

CONFIDENCE 2 Financial Education Program Evaluation.

**PRINCIPAL INVESTIGATOR:**

Name: [name]

DATE: 5/19/2025

**Indicate the origin of this protocol** (who conceived of and leads the development of the protocol regardless of funding):

Investigator initiated (*Investigator(s) developed protocol, regardless of funding*)

Industry (*Pharmaceutical, Device, etc.*) (*Industry developed protocol*)

Federal (*NIH, DOD, etc.*)

Cooperative Group (*SWOG, GOG, etc.*)

Other - Please specify: [Click here to enter text.](#)

Has this study been disapproved by or withdrawn from any other IRB?

Yes  No

If so, please explain: .

Does this study involve cancer research or cancer-related issues?

Yes  No

If yes, indicate the PRMC number: [Click here to enter text.](#)

Is this a student led study?

Yes  No

If yes, is the student:  Undergrad  Graduate Student  Other [Click here to enter text.](#)

If yes, is the project:  Capstone  Master's thesis  PhD dissertation

Other [Click here to enter text.](#)

Is this work part of a larger collaborative research project where more than one institution is participating in the research? (*In collaborative projects, data/specimens/results are often shared between researchers at the participating institutions, and they will publish together.*)

No  Yes

If yes, please explain.

We are collaborating with the University of Southern California, where the intervention is being administered as a part of a social service program for caregivers (USC Family Caregiver Support Program). USC may participate in the publication of findings but is not involved in data collection procedures, other than registration data used as a part of regular programming. We are also working with Amicus Brain Innovations as a study partner. Amicus Brain Innovations is responsible for building out technology components of the CONFIDENCE program. They will store data such as utilization data (e.g., receipt of text messages) from caregivers in the NeuViCare app that we are integrating into the intervention.

## 1.0 Funding

If this study is grant funded, is the money coming directly to CWRU from the study sponsor?

Yes  No  N/A, not grant funded

## 2.0 Objectives

**Directions: Describe the purpose, specific aims or objectives. Be sure to also include the hypothesis being tested.** The overall objective of this project is to test the feasibility, acceptability, and preliminary efficacy on an AI-enhanced psychoeducational intervention to reduce financial strain among Latino/Hispanic family caregivers to people living with dementia (PLWD) by supporting resource access called CONFIDENCE 2. The central hypothesis is that caregivers who participate in the CONFIDENCE intervention will report higher levels of resourcefulness and self-efficacy following participation in the CONFIDENCE intervention that will reduce financial strain among caregivers of PLWD.

## 3.0 Background

**Directions: Describe the relevant prior experience and gaps in current knowledge describing how this study will add to existing knowledge. Include any relevant preliminary data.** Family caregivers to people living with dementia encounter financial strain, including material, psychological, and behavioral components. Caregivers to PLWD also spend an average of \$8,978 per year out-of-pocket on caregiving expenses, which is around \$1000 more than caregivers to persons without dementia. Research findings support that caregiving places individuals at increased risk of poverty, due to factors such as reduced ability to engage in employment and spending down one's own savings to cover costs. Financial strain is also a risk factor for caregiver depression and burden which affects 1 in 5 family caregivers to PLWD. Financial strain disproportionately affects Latino/Hispanic family caregivers to PLWD. They spend 47% of their annual household income on out-of-pocket costs of caregiving, compared to 18% among non-Hispanic white, 34% among African American, and 22% among Asian American caregivers. These differences in out-of-pocket expenses are partially due to cultural preferences to provide care at home, such that Latino/Hispanic families provide more intensive care that is more likely to disrupt employment and increases out-of-pocket costs. Further, U.S. Latino/Hispanic households have a median net worth of \$52,190 (four times lower than U.S non-

Latino/Hispanic households), which makes it more difficult to absorb out-of-pocket costs when they occur. The impact of financial strain on Latino/Hispanic families is likely to grow substantially, given an anticipated 832% increase in the number of Latinos/Hispanics LWD in 2060. However in 2022 only two studies were found to examine intervention effects on financial strain of Latino/Hispanic caregivers.

To address the need for programs to reduce financial strain among Latino caregivers, we developed the Confidently Navigating Financial Decisions and Enhancing Financial Wellbeing in Dementia Caregiving (CONFIDENCE) program with support from AARP Foundation from 2020 to 2023. The original version of CONFIDENCE includes a 5-week, group-based psychoeducational intervention delivered by Zoom. Most data for the evaluation of the CONFIDENCE original program have been collected. Initial findings indicate high satisfaction with the program among participants (100% “Agree” or “Strongly Agree” they would recommend the program to other caregivers), but also lower-than-anticipated uptake and adherence. For example, only 51% of caregivers registering for CONFIDENCE at the USC Family Caregiver Support Center attended at least one session. Of those who attended at least one session, average attendance was 3.1 out of 5 sessions. These findings suggest high acceptability but limited feasibility.

The second version of CONFIDENCE aims to build on lessons learned from the original CONFIDENCE program with the goal of improving program feasibility prior to testing the program’s efficacy. To improve uptake and adherence, we have shortened the number of group-based Zoom discussion sessions from 5 to 4 to reduce the time required to participate. Content covered in the sessions removed from the core program will be delivered by asynchronous, technology-driven means. Participating caregivers will have a chance to decide which topics to focus on based on their current needs and will receive informational text messages covering these topics. Caregivers will also have access to a conversational AI assistant (“Keiko”) that will draw from hand-picked and trusted resources to devise answers to questions caregivers may have about topics such as how to find reduced-cost home modifications, how to prepare for retirement, and how to prevent financial scams. To support learning between discussion sessions, NeuViCare also will host a moderated community forum where caregivers can connect with other participating caregivers .

*Please add relevant references at the end of the protocol, not at the end of this section.*

## 4.0 Inclusion and Exclusion Criteria

**Directions: Describe how individuals will be screened for eligibility.**

Participants will be asked to either complete an online self-administered survey to determine their eligibility, or to complete eligibility questions by telephone.

**Using the tables below, describe the inclusion and exclusion criteria that will define who will be included and excluded in your final study sample.**

Inclusion	
1.	Age range: from 18 to not upper limit
2.	Has been at least 6 months since the care recipient began to experience dementia symptoms
3.	Person living with dementia meets stage 4 to 6 criteria on Global Deterioration Scale according to family caregiver
4.	Latino/Hispanic ethnicity

Exclusion	
1.	Individuals who plan to place their family member in a nursing home in the next 3 months
2.	Unreliable access to internet, tablet or smart phone, and email
3.	Does not agree to participate in at least 3 of the 4 group sessions and/or register for the NeuViCare app
4.	Unable to read and speak in English or Spanish

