**Satisfaction surveys.** To analyze Likert responses to satisfaction surveys, a percentage for each response will be provided. Each item will be compared to items collected for the initial CONFIDENCE study, as well as scores for items of CONFIDENCE between Spanish and English intervention.

**Attendance.** We will report the average number of sessions attended (range 0 to 4) and the standard deviation. Comparison on the number of sessions attended will be compared between the English and the Spanish sessions as well as between the earlier and current version of CONFIDENCE in the form of percentages to allow us to draw preliminary comparisons, given the different number of possible sessions to attend (3 vs. 5). The average number of sessions will be calculated both with and without accounting for make-up sessions. (i.e., giving credit for attendance in Session 1 if the caregiver attended the makeup session for this lesson.)

**App Utilization.** Usage data from NeuViCare™ Care and Resources Advisors will be reported in aggregate Individual-level data will be collected on the average number of text received, average interactions on the Community Hub, and average number of practice activities completed on NeuViCare.

**Fidelity.** Fidelity reports will be evaluated using total scores averaged across all CONFIDENCE sessions observed. Sub scores will be reported for adherence to the facilitator guide, participant experience, and quality of delivery. These will be reported separately for English and Spanish participants by using a percentage, as well as means and standards of deviation, to examine variability.

**Qualitative interviews.** Qualitative interviews will be transcribed verbatim, and for the ones conducted in Spanish, they will be previously translated. Transcription and translation of interviews conducted in Spanish will be by ASTA-USA. English Transcriptions will be done by GMR. A preliminary code book will be developed by at least two research members and will be refined prior to applying codes to the remaining interviews. At least two coders will analyze each transcript independently and will meet to compare the codes. The second round of coding will be conducted to integrate new codes if needed.

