## 24.0 Alternatives to Participation

**Directions: List other options to participation. If subjects will be compensated with extra course credit, the course instructor offering extra course credit must provide alternatives to earn extra course credit. The alternative assignment must require equal or less time and effort for the same amount of earned extra credit that you can earn through participation in research. If there are other available clinical treatments, what would be included if a subject continued on standard of care therapy. If there is a viable alternative you must list it in the consent.**

Participants may still participate in the CONFIDENCE program, regardless of study participation.

The alternative is for research subjects not to participate.

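### Exclusion 3 makes enrolled-sample attendance conditional on a promise to attend, so the comparison with version 1 can improve through selection alone

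*Combined protocol and SAP*

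**What the plan says.** Section 2.0 sets out to "test the feasibility, acceptability, and preliminary efficacy" of the intervention. Section 3.0 explains why there is a second version: in version 1 "only 51% of caregivers registering for CONFIDENCE at the USC Family Caregiver Support Center attended at least one session", and "Of those who attended at least one session, average attendance was 3.1 out of 5 sessions". Version 2 was designed "with the goal of improving program feasibility" before efficacy is tested.

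Exclusion 3 in Section 4.0 removes a caregiver who "Does not agree to participate in at least 3 of the 4 group sessions and/or register for the NeuViCare app".

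Section 17.0 (Attendance) then states: "We will report the average number of sessions attended (range 0 to 4) and the standard deviation". It also plans a comparison "between the earlier and current version of CONFIDENCE in the form of percentages to allow us to draw preliminary comparisons". Section 12.0 describes the same comparison and refers to attendance by participants. The design in Section 12.0 is single-arm.

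The programme is open to people outside the study. Section 24.0 says "Participants may still participate in the CONFIDENCE program, regardless of study participation", and Section 10.0 says the same.

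**The concern.** The entry rule asks about the behaviour that the feasibility analysis later measures. Caregivers who say at screening that they cannot manage three sessions do not enter the study, so they cannot lower its attendance figure. With no concurrent control, the comparison with version 1 is the only yardstick for better adherence. Section 3.0 describes the version 1 figures for registrants and attenders and mentions no pledge.

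High attendance in the enrolled sample could then be read as showing that a shorter, app-supported format works for Latino/Hispanic caregivers, when part or all of the gain reflects who was let in. Nothing in Section 17.0 guards against this. It names no population for the attendance mean, gives no count of people screened out under exclusion 3, and has no counterpart to the 51% uptake figure.

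The wording adds a second problem. A caregiver who accepts the sessions but declines the app is excluded if refusing either commitment is enough, and eligible if both must be refused. Two screeners could treat the same person differently.

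**Working it through.** **Figures on one scale.** Version 1 attendance among those attending at least once (Section 3.0): 3.1/5 = 62%. Minimum session pledge (Section 4.0): 3/4 = 75%. The pledge lies 75 − 62 = 13 points above the benchmark.

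**Simple bound.** Suppose a share c of enrolled caregivers attends exactly the pledged minimum and the rest attend as in version 1. Expected attendance is 62% + c × 13 points: 62% at c = 0, about 65% at c = 0.25, 68.5% at c = 0.50 and 75% at c = 1.

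**Model with no programme effect.** Each caregiver has a personal attendance probability p from a beta distribution. It is calibrated so that mean attendance over 5 sessions, among those attending at least one, is 3.1. The between-person correlation is not in the documents and is assumed at 0.1 to 0.5. The same caregivers are then offered 4 sessions, under one of three assumed screening rules:
- A: the chance of agreeing equals the person's own chance of attending at least 3 of 4, which is 4p³(1 − p) + p⁴;
- B: only those with p ≥ 0.50 agree;
- C: only those with p ≥ 0.75 agree.

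Expected attendance among those attending at least one session:

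| Correlation | No pledge | Rule A | Rule B | Rule C |
|---|---|---|---|---|
| 0.1 | 63.4% | 69.2% | 68.5% | 81.7% |
| 0.2 | 63.8% | 73.7% | 72.7% | 85.0% |
| 0.3 | 64.2% | 77.0% | 75.9% | 87.4% |
| 0.5 | 64.8% | 81.9% | 80.6% | 90.5% |

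Against the no-pledge column, rules A and B add 68.5 − 63.4 = 5 points at the low end and 81.9 − 64.8 = 17 at the high end. Against the published 62%, the same cells differ by 6.5 to 20 points. The strict rule C adds 18 to 26 points over no pledge. If agreeing is unrelated to p, every cell returns to the no-pledge column and the gain is zero.

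**Denominators.** The 3.1 of 5 leaves out people with no sessions, while the version 2 mean runs from 0 to 4 and so includes them. That works against version 2. In the model without a pledge, counting zeros gives 60.2% at correlation 0.1 and 41.9% at 0.5. The two versions are therefore not on the same denominator even before selection is considered. Section 17.0 also gives the possible sessions as 3 versus 5, against four sessions elsewhere; these passages must be reconciled, because that count is the divisor of the percentage.

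**Data for a registrant-wide figure.** Facilitators record attendance at each session (Section 12.0), Eventbrite data are downloaded whether or not the registrant joins the study (Section 16.0), and characteristics of non-study participants are on the data list (Section 15.0).

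**The case against.** The strongest reply is that a pledge is not adherence. Enrolled caregivers can still attend anything from 0 to 4 sessions, and on the permissive reading of and/or someone who agrees only to register for the app enters with no session promise. This stands: inflation is possible, not certain, and any range must start at zero.

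A reader might seek a firmer figure by giving every caregiver a 62% chance per session and dropping those who attend fewer than three, which yields 82%. That is not supported. If everyone has the same propensity, no screening question can separate future attenders from the rest, and that calculation removes people on attendance that has not yet happened.

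A reader might also infer that the problem persists whatever denominator is used. It does not. If attendance is computed over all programme registrants, exclusion 3 does not select that group. The plan does not name the population, and Section 12.0 speaks of participants, so the gap is real but can be closed by stating it.

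Requiring willingness to take part is a defensible choice when preliminary efficacy is also an aim and only 42 caregivers are to be recruited. The cross-version comparison is labelled preliminary and carries no test or threshold. These points argue for keeping the criterion. They do not remove the need to say what the enrolled figure is conditional on.

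The app side is weaker. Section 17.0 reports texts received, Community Hub interactions and practice activities, not registration itself, and Section 3.0 presents the app as new in version 2, so there is no cross-version app gain to inflate.

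**Conclusion.** The concern holds for attendance in the enrolled sample and for its comparison with version 1. Both are conditional on a stated intention to adhere, and both can look better with no programme effect. The size cannot be derived from the documents: zero if the pledge does not predict attendance, roughly 5 to 20 points if it tracks propensity under the moderate rules assumed above, and more under a strict cut. The documents do not say whether version 1 had the same rule; if it did, the cross-version bias shrinks, though the stand-alone result remains conditional on the pledge.

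Two stronger readings are not supported. One is that the pre-post results for resourcefulness, self-efficacy and financial strain are biased by the pledge: it does not by itself create change from baseline, and only limits to whom the results apply. The other is that the criterion must be deleted. The document is dated 5/19/2025 and recruitment was planned from March 2024 to August 2025, so deletion would come about 14 months into an 18-month window and mix two eligibility rules in a small single-arm sample.

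**What to change.** Keep the criterion and change the reporting:

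1. In Section 17.0, make the cross-version comparison on version 1's denominators for all programme registrants: the percentage of Eventbrite registrants attending at least one session (against 51%), and mean attendance among those attending at least one (against 62%). Show the enrolled-sample figure beside it and name the population of each.
2. Count caregivers screened out under exclusion 3 by reason (sessions or app) and report them as non-uptake in the study's feasibility result. Any who joined the programme anyway also appear in the registrant figures.
3. State that the enrolled-sample feasibility result applies to caregivers who pre-commit.
4. Replace and/or in exclusion 3 with one explicit rule, and record how it has been applied so far.

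The cost is a short amendment, a line or two in the screening table, and some work linking attendance to registrations from sources the protocol already lists. Reported attendance and uptake may be less favourable. The comparison will still be historical: Section 8.0 notes, for example, that age eligibility widened from 50+ to 18+.

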## 5.0 Number of Research Participants

**Directions: Indicate the target number of research participants to be accrued locally, and, if this is a multi-site study, indicate the total number of research participants to be accrued across all sites.**

**Example language that can be used:** *We will enroll 25 subjects at CWRU and plan to enroll 150 subjects study wide.* We will recruit 42 family caregivers to account for the anticipated 20% attrition before and after participation in CONFIDENCE 2. Moreover, at least 12 participants will complete qualitative interviews.

## 6.0 Special/Vulnerable Populations

*Indicate specifically if you will include each of the following special populations by checking the appropriate box:*

- Adults unable to consent**
- Minors (infants, children, teenagers)**
  - Wards of the state (e.g. Foster Children)
- Pregnant Women** (only if targeted)
- Neonates**
- Neonates of Uncertain Viability**
- Employees**
- Prisoners**
- Illiterate Individuals**
- Non-English Speaking**
- Students**
- None**

1. If the research involves students or employees, describe how you will recruit so that:
  - a) Employers or educators do not know if someone participated (until after grades have been assigned in the case of educators)
  - b) Employers or educators do not *directly* recruit their own students or employees, and anything else to prevent feelings of coercion to those subordinate to their employer or educator.

2. If the research involves individuals that are included in a special/vulnerable population, describe the additional safeguards included to protect the rights and welfare of the individuals for each population indicated. [Click here to enter text.](#)
3. If excluding pregnant women, illiterate or non-English speaking individuals, provide a scientific rationale for the exclusion. Inconvenience or cost is not an acceptable rationale. Persons who are illiterate are excluded from the study due to an inability to engage with the program materials, such as the written workbook and text materials.

## 7.0 International information

- This is not an international study – [please leave rest of this section blank.](#)
- We will be conducting this research at the following international sites:  
[Click here to enter text.](#)
- We are recruiting participants outside of the US from the following locations:  
[Click here to enter text.](#)
- We are sending data outside of the US to the following locations:  
[Click here to enter text.](#)
- We are receiving data from outside of the US from the following locations:  
[Click here to enter text.](#)

## 8.0 Recruitment Methods

*Note: Attach all applicable recruitment materials to the last section of the Smart form under “Recruitment Materials.”*

1. Which of the following methods will be used to recruit research participants? – [Select all that apply](#)
  - Email
  - Phone call
  - Letter
  - Advertisement (e.g., poster, flyer, etc.)
    - I attest that advertisements will only be placed with permission
  - Social media
    - Indicate the platform(s): Facebook
    - I attest that recruitment information will only be posted with permission
  - Other. *Please specify:* [Click here to enter text.](#)
2. Describe when, where, how and by whom potential research participants will be recruited. Individuals involved in recruitment should be identified by role and not by name (e.g. study coordinator, co-investigator, research assistant).  
**Information about CONFIDENCE will be shared by email blast sent to caregivers in the USC FCSC mailing list. USC FCSC Family Consultants will also share information about the program with clients who may benefit (See Talking Points document.).**  
 Caregivers may also learn about the study on the Alzheimer's Association TrialMatch

HRP- 503SBER	TEMPLATE: CWRU SBER Protocol		
Approved:	09/2021	Prior Version:	05/2021

site. Participants who register on Eventbrite and indicate interest in learning more about the study will receive calls and emails from the study team with information about the study. If interested, eligibility screening will be conducted by phone and they will be sent an email with a REDCap consent form to review. Participants who complete the eligibility screening online will receive a link to the consent form and a telephone confirmation. Once enrolled, participants will receive a baseline survey up to 3 weeks before their first scheduled CONFIDENCE session.

3. Describe the feasibility of recruiting the required number of suitable research participants within the agreed recruitment period. For example, how many potential research participants do you have access to?

The anticipated recruitment period will begin in March 2024 to August 2025. We aim to enroll 5-6 caregivers per cohort. Each cohort will take 4-5 weeks to complete. We aim to use the same recruitment approach as was done in the original CONFIDENCE study, relying heavily on the USC FCSC client list. USC FCSC serves over 500 caregivers yearly, among whom 60% are Latino/Hispanic and 38% care for someone living with AD/ADR. Although recruitment into the initial study was far lower than anticipated, multiple factors are expected to contribute to higher enrollment in this study, including 1) reduced burden of participation in the intervention (e.g., reduction of synchronous sessions from 5 to 4), 2) reduced burden of study participation (e.g., removal of daily spending diary component), and 3) expansion of age eligibility criteria from caregivers ages 50+ to 18+ in the current study. Further, we have expanded our recruitment approach during the initial CONFIDENCE study.

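### Age eligibility widened from 50+ to 18+ between versions, but the planned version comparison of attendance and satisfaction takes no account of age

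*Combined protocol and SAP*

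**What the plan says.** All references are to the combined protocol and SAP.

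- **Eligibility.** Section 8.0 lists three reasons to expect better enrolment than in the original study. The third is an "expansion of age eligibility criteria from caregivers ages 50+ to 18+ in the current study". Section 4.0 confirms the current criterion: "Age range: from 18 to not upper limit".
- **Satisfaction.** Section 17.0: "Each item will be compared to items collected for the initial CONFIDENCE study".
- **Attendance.** Section 17.0 compares attendance "as well as between the earlier and current version of CONFIDENCE in the form of percentages to allow us to draw preliminary comparisons". The reason it gives for using percentages is the different number of sessions on offer. Section 12.0 also plans an attendance comparison across versions.
- **Version 1 results.** Section 3.0 reports that "only 51% of caregivers registering for CONFIDENCE at the USC Family Caregiver Support Center attended at least one session". It adds: "Of those who attended at least one session, average attendance was 3.1 out of 5 sessions".
- **Purpose of version 2.** Section 3.0 says the redesign is meant to raise uptake and adherence, and so feasibility, before efficacy is tested.

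No section limits the version comparison to the ages both studies admitted, stratifies or adjusts it by age, or names the change in age criterion as a limitation.

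**The concern.** The two studies admitted different populations by design. Caregivers aged 18-49 can enrol in the current study and could not enrol in the original one. Section 8.0 expects the wider range to bring in more participants, so the new group is unlikely to be empty. If younger caregivers attend more or less often, or rate the program differently, the all-ages contrast adds that difference to any effect of the shorter, app-supported format.

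This matters because better feasibility than version 1 is the stated reason for the redesign. The primary analyses compare each follow-up with baseline within the current study, so they cannot show whether attendance improved on version 1. The cross-version comparison is the planned quantitative result that speaks to that aim. A reader could credit the redesign with a gain, or blame it for a loss, that came from the change in who was eligible.

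**Working it through.** The plan gives no figure for this comparison, so there is none to reproduce. The check has three parts: the version 1 anchor, the possible shift from age mix, and the numbers left after an age restriction.

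**Inputs from the documents**
- Version 1 attendance: 3.1 of 5 sessions among those attending at least one (Section 3.0).
- Version 2 sessions: 4 (Sections 3.0 and 12.0).
- Planned enrolment: 42, with 20% attrition anticipated (Section 5.0).

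**Inputs assumed, because the documents do not give them**
- s, the share of version 2 caregivers under 50: 10%, 25% or 50%.
- d, the attendance difference between under-50s and those 50+: 5 to 20 percentage points, in either direction.

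**Anchor.** 3.1 / 5 = 62%. The same percentage in version 2 would be 0.62 × 4 = 2.48 sessions. One session of four is 25 points.

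**Shift from age mix.** Let m be mean attendance in version 2 caregivers aged 50+. The all-ages mean is (1 − s) × m + s × (m + d) = m + s × d. If version 1 holds only caregivers aged 50+, the all-ages contrast differs from the 50+ contrast by s × d.

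| s (assumed) | d = 5 | d = 10 | d = 20 |
|---|---|---|---|
| 10% | 0.5 | 1.0 | 2.0 |
| 25% | 1.25 | 2.5 | 5.0 |
| 50% | 2.5 | 5.0 | 10.0 |

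The entries are percentage points. The sign follows the sign of d, which is unknown.

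**Numbers left in a 50+ contrast.** 42 × (1 − s), then × 0.80 for attrition:
- s = 10%: 37.8 enrolled, 30.2 after attrition.
- s = 25%: 31.5 enrolled, 25.2 after attrition.
- s = 50%: 21 enrolled, 16.8 after attrition.

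**Precision.** With an assumed attendance SD of 30 points (not in the documents), the 95% half-width for the version 2 mean is 1.96 × 30 / √n. That is 9.1 points with all 42, and 9.6, 10.5 and 12.8 points with 37.8, 31.5 and 21. The restriction widens the interval by about 0.5 to 3.8 points.

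**Who is in the version 1 figures.** Section 8.0 gives 50+ as the age criterion of the original study. The Section 3.0 results, however, describe people who registered for the program. In the current trial the program is open to caregivers who decline the research (Sections 10.0 and 24.0). Section 16.0 says registration data are downloaded whether or not a registrant joins the study, and were also collected in the previous study. The documents therefore do not show that every version 1 attendee was 50 or over. Section 17.0 does not say whether the version comparison covers enrolled participants or all attendees.

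**The case against.** The strongest case against the point has five parts.

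1. **No bias has been shown.** A reader might infer that the contrast is confounded by age. The documents support only that it could be: no section links age to attendance or satisfaction, and the shift rests wholly on assumed inputs. This stands.

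2. **Version 1 may include people under 50.** A reader might infer that caregivers aged 18-49 appear only on the version 2 side. That follows for enrolled study participants but not for registrants or attendees, whom the Section 3.0 figures describe. Restricting version 2 alone to 50+ could then create an imbalance. This stands, and it is why any restriction must apply to both versions within one defined analysis set.

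3. **The comparison has a modest role.** It is descriptive, the attendance part is labelled preliminary, and no test or success rule depends on it. A reader might infer that it is the trial's only evidence on the redesign, but the qualitative interviews also inform acceptability. This lowers the weight of the point. It does not remove it, because better feasibility is the declared aim of version 2.

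4. **One satisfaction result cannot be inflated.** All version 1 participants agreed or strongly agreed that they would recommend the program (Section 3.0). Combined agreement on that item cannot rise, so younger caregivers cannot produce a false gain there. They could contribute to a fall.

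5. **An age restriction does not make the versions comparable.** A reader might take a 50+ contrast as like for like. It is not. The version 1 mean counts only people who attended at least once, while for version 2 the plan says: "We will report the average number of sessions attended (range 0 to 4) and the standard deviation". Version 2 also excludes caregivers who do not agree to attend at least three of four sessions and/or register for the app, and the documents do not say whether version 1 had such a rule. This stands in full.

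**Conclusion.** The point holds as a modest one. Study eligibility changed from 50+ to 18+, the version comparison of attendance and satisfaction ignores this, and a difference could partly reflect the added younger caregivers. For attendance, the shift from age mix alone is about 0.5 to 10 points in either direction. That assumes 10-50% are under 50, that they differ from older caregivers by 5-20 points, and that version 1 holds only caregivers aged 50+. None of these is in the documents. For satisfaction they offer no basis for a size. The documents do not support the stronger conclusion that the comparison is biased, or biased in a known direction. The primary pre-post outcomes are unaffected. The change is worth making because it is cheap and uses age, which is an eligibility criterion and is listed in Section 28.0 among the participant characteristics to be reported.

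**What to change.** In Section 17.0, under Satisfaction surveys and Attendance (and in the matching Section 12.0 text):

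1. State one analysis set and use it for both versions: either enrolled study participants, or all registrants or attendees whose age is recorded.
2. Show the version comparison in caregivers aged 50+ in both versions, beside the all-ages figure and the version 2 figure for ages 18-49.
3. Do not credit a difference to the redesign unless the 50+ comparison points the same way.
4. Name the change in age eligibility as a limitation.

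**Cost.** A few sentences and extra table columns. Enrolled participants need no new data; for registrants, the comparison is limited to those with a recorded age. The 50+ contrast is less precise, with about 21 to 38 of the 42 if 10-50% are under 50 (assumed).

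**What this does not cure.** Three other differences need their own correction:
- The version 1 mean is conditional on attending at least one session, while version 2 counts from zero.
- Version 2 has an entry requirement on attendance and/or app registration.
- The attendance paragraph gives the session counts as three versus five, although version 2 has four sessions elsewhere. The count matters: 2.48 sessions is 62% of four but 2.48 / 3 = 82.7% of three. These passages must be reconciled.
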